Participants will complete home-based baseline and post-treatment study visits when the child is 2 months and 9 months of age. Families randomized to the intervention condition will participate in six treatment sessions delivered as monthly 1-hour home or virtual visits based on the desires, interests, and needs of families, when the child is 3, 4, 5, 6, 7, and 8 months of age in addition to participation in the standard ECS visits. Given the program's target of behavior change and use of behavioral strategies, interventionist-delivered HEMI sessions will be provided by advanced clinical psychology doctoral students (supervised by a licensed clinical psychologist, PI [name]) accompanied by support staff. Two peer counselor-led sessions will be delivered as 1-hour home or virtual visits, based on the desires, interests, and needs of families and peer counselors, when the child is 5 and 8 months of age. Families in the control condition will receive the standard ECS content and complete baseline and post-treatment visits.

6.3 Describe procedures being performed to monitor subjects for safety or minimize risks.

Based on the size ($n = 30$) and complexity of the trial (e.g., unblinded trial) and the minimal risk of the study intervention to participants, this study will utilize an independent safety monitor (ISM) whose primary purpose will be to provide guidance regarding adverse events and safety issues. The ISM will be a medical expert (e.g., pediatrician, nurse) who is independent of the study and able to provide external and unbiased evaluation through consultation pertaining to safety issues. This person will be available in real-time on an as-needed basis should any concerns regarding adverse events or other safety issues arise. The ISM will be identified during the study start-up phase. The ISM will review relevant participant safety data and make recommendations regarding continuation, modification, or termination of the trial due to safety risk. Communication with the ISM will occur on an as-needed basis when safety concerns arise as well as annual meetings with the study PI to discuss overall trial safety data.

TEMPLATE: RESEARCH PROTOCOL

| NUMBER | ACTIVE DATE | PAGE |
|---------|-------------|----------|
| HRP-503 | 02-04-2020 | 13 of 44 |

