The following potential adverse events will be assessed throughout the study period: occurrence of choking episodes during infant feedings (at each study visit and interventionist-led treatment session), growth faltering (monitored at each interventionist-led treatment session for infants in the treatment condition; length and weight will be monitored for all participants [i.e., treatment and control] at baseline and post-treatment), and unexpected adverse events.

Study participants will be informed of any changes to the known risks and benefits of participating in the current study, including if it is identified that treatment participants are at greater risk for adverse events. If participants in the treatment arm experience greater adverse events, possible discontinuation of the study or modification of the intervention will be considered under the guidance of the ISM.

6.5 Where applicable, list and describe the data collection tools such as surveys, data collection forms, etc. All tools described should be uploaded in the RAP Smart Form on the Local Site Documents page unless they are standardized, validated tools.

Demographics Form. Participants in both the intervention and GLA methodologies will complete a demographics form. There is a separate demographic form for each of these methodologies because the interventionist participants will be asked additional demographic details about their participating child, while GLA participants will only report their own adult demographics.

Maternal Feedback on Intervention: Maternal Feedback on the Intervention will be obtained through a quantitative survey and a qualitative interview. The quantitative survey consists of Likert scale ratings on whether they perceived the intervention as suitable, occurring at the right time, being presented clearly, and helpful; mothers will also rate satisfaction with the intervention and their confidence in implementing the recommendations made by the study team. Qualitative interviews will be conducted with each family by a research staff member who was not the study interventionist (to prevent potential bias) to obtain feedback regarding additional information that would be helpful to add to the program, content that was not helpful and could be eliminated from the program, other changes they would like to see to the program, and aspects they would like to see stay the same about the program.

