Peer Counselor Feedback on the Intervention: Interviews will be completed with peer counselors after all study participants have completed treatment. Open-ended questions will be asked such as: What aspects of the intervention did you feel were most helpful for families? What are additional things not currently offered in the intervention that you think could be helpful to families? Did you feel adequately

TEMPLATE: RESEARCH PROTOCOL

| NUMBER | ACTIVE DATE | PAGE |
|---------|-------------|----------|
| HRP-503 | 02-04-2020 | 14 of 44 |

trained to provide the intervention? How do you feel participants utilized your role as a peer counselor? How could the peer counselor sessions be improved?

Infant Anthropometrics: Infant weight and length will be measured in duplicate at each in person treatment and study visit using a mobile digital SECA baby scale and portable infant length board. The scale will be calibrated using a known weight, and will be zeroed prior to assessment. Infants will be weighed in a clean diaper without clothes. The length board has a stable headboard and a moveable foot board, and will be placed on a flat, hard surface. All length measurements will be taken using the right leg, with assistance from the mother as needed to hold the infant still while the right leg is extended flat and the foot flexed against the foot board. Weight measurements will be taken to the nearest 1.0 gram and length measurements to the nearest 0.5 cm. Infant BMI standardized for age and sex will be calculated from the WHO 2005 growth standards.

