Aim 1: For aim 1, participants will complete demographic information in an online survey. In this survey, they will also need to indicate their email address in order to receive their electronic gift card for participation in the group. They will also be asked on the form their interest in participating in subsequent action planning groups, and we will use their email to contact interested participants. In order to secure confidentiality of demographic data, we will remove the potentially identifying email address from the database as soon as the groups are completed.

Aim 2: Demographic information and maternal quantitative feedback on the intervention will be obtained through an online survey using the data capturing system REDCap. Maternal qualitative feedback on the intervention will be obtained via interview at the post-treatment study visit, and peer counselors will also complete qualitative interviews with research staff to provide feedback on the intervention. All data will be identified with ID numbers only, and the list linking ID numbers to participant names will be kept in a password-protected document separate from all other participant data on a password protected computer and secure server. Only study staff will have access to participant identifiable information during the study.

17.3 Describe any procedures that will be used for quality control of data collection.

Infant anthropometric measurements will be recorded on paper-and-pencil forms, and dietary information will be retrieved via phone interview. All other maternal-report measures will be completed through a REDCap survey on a tablet. REDCap software is administered by the Center for Clinical and Translational Science and Training (CCTST). The REDCap survey and database will be built by study staff, and tested for accuracy until all issues have been resolved prior to moving the survey into production for data collection. Only study staff will have access to the REDCap database.

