18.3 How will the safety information will be collected?

Adverse event data collection sheets have been established for recording adverse events reported by participants. These forms will be completed at each treatment session (i.e., Session 1, Session 2, Session 4, Session 5, and Post-Treatment) or study visit conducted by a research staff interventionist (i.e., not done at peer counselor-led sessions). For choking episodes, the date of the episode, details of the episode (e.g., food being eaten, situation in which eating occurred), and any intervention required (e.g., medical attention) will be recorded. For growth faltering, caregivers will be asked to describe their concerns regarding their child's growth. Additionally, infant weight will be recorded at each study visit and treatment session (i.e., Session 1, Session 2, Session 4, Session 5, and Post-Treatment) conducted by a research staff interventionist (i.e., not done at peer counselor-led sessions). All other potential adverse events reported to study staff will also be documented.

18.4 The frequency or periodicity of review of cumulative data.

Regularly scheduled meetings between the ISM and PI will occur annually. Emergency meetings will be scheduled by the PI if immediate concerns arise between regularly scheduled meetings.

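### Nothing keeps the interventionist who treated a family from taking the 9-month weight and length behind the primary BMI outcome, although other assessments in this unblinded trial are protected

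*Protocol*

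**What the plan says.** **Who conducts the visit.** Protocol 18.3 states that "infant weight will be recorded at each study visit and treatment session" and then lists the contacts, ending with "Session 4, Session 5, and Post-Treatment) conducted by a research staff interventionist". Protocol 6.2 sets "baseline and post-treatment study visits when the child is 2 months and 9 months of age", so Post-Treatment is the 9-month outcome visit.

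**Who measures.** Protocol 17.5 assigns weight and length to research staff, with no role and no masking. Protocol 6.5 (Infant Anthropometrics) describes duplicate readings, a calibrated digital scale, and "length measurements to the nearest 0.5 cm", taken with the leg extended and the mother helping as needed. It does not name the measurer either.

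**Blinding.** Protocol 6.3 refers to the size and "complexity of the trial (e.g., unblinded trial". Protocol 6.2 says that "interventionist-delivered HEMI sessions will be provided by advanced clinical psychology doctoral students", who are accompanied by support staff.

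**Protection elsewhere.** Protocol 6.5 blinds the diet-recall interviewers to study condition. It also has the maternal feedback interview done "by a research staff member who was not the study interventionist (to prevent potential bias"). Protocol 17.2 adds: "Maternal qualitative feedback on the intervention will be obtained via interview at the post-treatment study visit". Protocol 17.3 has session recordings coded by staff who are not providing the intervention.

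**What depends on it.** SAP section 1 makes infant BMI the primary outcome, both as the percentage at or above the 85th percentile and as change in percentile. SAP section 3 says the pilot is underpowered but will allow an effect size to be estimated for larger studies.

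**The concern.** The protocol accepts in three places that people who deliver the intervention should not assess its results. The measurement behind the primary outcome has no such rule, and the one section that says who conducts the 9-month visit names an interventionist.

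Weight on a digital scale leaves little room for judgement. Length leaves more, because an infant has to be held still and straightened, and length enters BMI squared. Under 6.5, infants are also measured at each in-person treatment visit. A treating interventionist may therefore have measured the same infant several times before 9 months, while a control infant has been measured only at baseline. Expectation, or anchoring on previous readings, could act in the treated arm alone. Duplicate readings do not remove this if the same unmasked person takes both.

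Random measurement error would mainly add noise. An error confined to one arm moves the between-arm difference itself, and that difference is what the pilot is meant to hand on to a larger trial.

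**Working it through.** **1. Do the documents name or mask the measurer?** The relevant sections, side by side:

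| Assessment | Who does it | Section |
|---|---|---|
| Diet recall (secondary outcome) | Interviewers blinded to condition | Protocol 6.5 |
| Maternal feedback interview | Not the study interventionist | Protocol 6.5, 17.2 |
| Fidelity coding | Staff not giving the intervention | Protocol 17.3 |
| 9-month weight and length (primary outcome) | Research staff, at a visit listed as interventionist-conducted | Protocol 17.5, 18.3 |

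Only the last row has neither masking nor separation from treatment.

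**2. Inputs for an illustration.** The plan gives no figure for measurement bias.
- From the documents: 31% at or above the 85th percentile at 9 months; mean (SD) change 19.6 (29.3) percentile points; 15 per arm (SAP section 3); length read to 0.5 cm (Protocol 6.5).
- Assumed: length 71 cm; BMI coefficient of variation (CV) 7% to 9%; BMI z-scores normal with SD 1; every treated infant and no control read 0.5 cm too long.

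As a check on the planning inputs, a two-sided t-test with difference 19.6, SD 29.3 and 15 per arm has 42.4% power, against the SAP's 43%.

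**3. Effect on BMI.** (71/71.5)² − 1 = −1.39%. Over lengths of 66 to 74 cm, the fall is 1.5% to 1.3%.

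**4. In SD units.** 0.0139/0.09 = 0.155 and 0.0139/0.07 = 0.199.

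**5. Effect on the binary outcome.** A 31% rate puts the cut-off 0.496 SD above the group mean. After the shift:
- CV 9%: P(Z > 0.496 + 0.155) = 25.8%
- CV 7%: P(Z > 0.496 + 0.199) = 24.4%

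The loss is 15 × (0.310 − 0.258) = 0.8 to 15 × (0.310 − 0.244) = 1.0 infants of 15.

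**6. Effect on the mean percentile.** The 85th percentile is z = 1.036, so the group mean is 1.036 − 0.496 = 0.540. The mean percentile is 100 × Φ(mean/√2).
- No shift: 100 × Φ(0.540/√2) = 64.9
- CV 9%: 100 × Φ((0.540 − 0.155)/√2) = 60.7, a fall of 4.1 points (unrounded)
- CV 7%: 100 × Φ((0.540 − 0.199)/√2) = 59.5, a fall of 5.3 points (unrounded)

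As a share of the planning effect: 4.1/19.6 = 21% and 5.3/19.6 = 27%.

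**7. Smaller error.** With 0.25 cm, BMI falls (71/71.25)² − 1 = −0.70%. The rate falls to 28.3% to 27.6% and the mean percentile by 2.1 to 2.7 points, about half of the above.

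**8. Effect on the test.** With SD 29.3, 15 per arm and no true effect, a between-arm shift of 2, 5 or 10 percentile points raises the rejection rate of the two-sided 5% t-test to 5.4%, 7.4% or 14.7%. The estimate moves by the full shift. The damage is mainly to the estimate, not to the error rate.

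**The case against.** **The measurer is an inference.** Section 18.3 is about collecting safety data. It says who conducts the visit, not who takes the reading, and its weight sentence does not mention length. The qualifier seems meant to exclude peer-counselor sessions, and the list treats Post-Treatment loosely as a session. Support staff accompany interventionists to sessions. All of this stands. A reader might infer that the interventionist will measure the infants she treated. The documents do not say so; they only fail to rule it out.

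**The feedback interviewer is not a ready-made assessor for both arms.** A reader might infer that a non-interventionist already attends every 9-month visit. The interview asks about the intervention, and control families receive standard ECS content only, so attendance is assured only for treated families. If this person measured only where an interview was due, the assignment would itself reveal the arm. This stands and limits the fix.

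**Striking Post-Treatment from the list in 18.3 would do harm.** The same list governs the adverse-event forms, and 6.3 requires choking to be assessed at each study visit. The entry should stay.

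**The size is easily overstated.** An infant at the 50th percentile would fall 6 to 8 points, which a reader might set against 19.6 as 31% to 40%. That divides the shift of one infant, on the steepest part of the percentile scale, by a group mean. The mean shift is the proper comparison. A uniform 0.5 cm error in one arm has no basis in the documents, and duplicate readings, calibration and a standard length procedure all work against it.

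**The trial is openly unblinded and underpowered.** This is true, but openness about blinding does not remove assessor bias, and the pilot's use for effect-size estimation makes bias in the estimate more relevant.

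**Conclusion.** The point holds as a missing safeguard. Section 18.3 puts the 9-month weight at an interventionist-conducted visit, 17.5 leaves the measurer generic, the trial is unblinded, and no section separates treatment from measurement of the primary outcome. That the interventionist knows the arm of the families she treated is an inference, but a safe one.

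The documents do not show that biased measurement is planned or will occur. The illustrated size (about 1 infant in 15, and 4 to 5 percentile points on average) depends wholly on the assumed one-arm 0.5 cm error, the 71 cm length and the CV of 7% to 9%. It shows that one recording step in length, if it were systematic in one arm, would be a material part of the effect the trial hopes to see. The point is worth acting on because the remedy is inexpensive: a cheap improvement, not a flaw that invalidates the design.

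**What to change.** State in Protocol 6.5, 17.5 and 18.3 that, in both arms, 9-month weight and length are taken by an existing study staff member who did not deliver HEMI to that family. Support staff who did not attend that family's sessions, or a fidelity coder who has not coded them, would serve. The feedback interviewer would serve only if the same role is scheduled for control families.

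Take the measurements first at the visit, before any interview, without telling the measurer the allocation and without sight of earlier readings. Keep Post-Treatment in 18.3 as a contact for adverse-event forms and weight recording; change only who takes the outcome measurement.

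The cost is protocol wording and some scheduling of existing staff, chiefly for control visits. No new assessor post is needed. Mothers may still reveal the arm, so masking will be partial; what the change reliably removes is measurement by the person who treated the family.

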18.5 Who will review the data?

An independent safety monitor (ISM) will be identified during the start-up phase of the study timeline and will provide guidance regarding adverse events and safety issues.

18.6 The statistical tests for analyzing the safety data to determine whether harm is occurring.

ANOVAs will examine the number of adverse events in the control versus intervention group.

18.7 Any conditions that trigger an immediate suspension of research.

Study participants will be informed of any changes to the known risks and benefits of participating in the current study, including if it is identified that treatment participants are at greater risk for adverse events. If participants in the treatment arm experience greater adverse events, possible discontinuation of the study or modification of the intervention will be considered under the guidance of the ISM. Any action resulting in temporary or permanent suspension of the study will be immediately reported to the funding agency program official.

| NUMBER | ACTIVE DATE | PAGE |
|---------|-------------|----------|
| HRP-503 | 02-04-2020 | 24 of 44 |

| | |
|--|--|
| 19.0 PARTICIPANT PRIVACY | 19.1 Describe the provisions to protect participants' privacy and to minimize the intrusiveness of the study questions or procedures. |
| | Participant responses will be linked to their study ID # rather than their names. Only study staff will have access to the file linking study ID# and names. All identifying information as defined by the HIPAA Privacy rule will be removed (e.g., birthdates) 2 years after the research ends. Study staff will also receive training on information related to confidentiality and session content management. This training includes education about treatment content (e.g., responsive feeding, infant obesity risk factors) and specific treatment recommendations, strategies for active listening, skills for asking sensitive questions, and how to manage sensitive/confidential information. |
| 20.0 COMPENSATION FOR RESEARCH RELATED INJURY | 20.1 For more than minimal risk research, describe the available compensation in the event of research-related injury. |
| | Not applicable. |
| 21.0 ECONOMIC BURDEN TO SUBJECTS | 20.2 Provide a copy of contract language relevant to compensation for research-related injury. |
| | Not Applicable |
| 21.0 ECONOMIC BURDEN TO SUBJECTS | 21.1 Describe any costs that subjects may be responsible for because of participation in the research. |
| | There are no anticipated costs that participants may be responsible for. |

| | | |
|---------------------|--|--|
| 22.0 CONSENT | 
22.1 Obtaining consent – Check applicable and complete the corresponding section(s). Please note, sections 23-28 each apply under different circumstances. Please complete the correct sections as checked in this section (e.g. if you do not request a waiver of documentation of consent, do not complete section 24)
 | |
| |  | The research team will obtain written consent from all subjects. (Complete section 23) (HRP-502M TEMPLATE Medical Informed Consent or HRP-502S TEMPLATE SBER Informed Consent or HRP-502V TEMPLATE VA Informed Consent) |
| |  | The research team will obtain consent from all subjects but is requesting a waiver of documentation (signature) of consent. (Complete sections 23 and 24) (HRP-502I TEMPLATE Information Sheet) |
| |  | The research team is requesting a waiver or alteration of the consent process. (Complete section 25) |
| |  | The research team is requesting Exception from Informed Consent for emergency research. (Please complete the EFIC supplement document and upload under number 3 on the local site documents page in RAP) |
| |  | The research team will enroll Non-English-speaking subjects and obtain consent (written or otherwise). (Complete sections 23 and 26) |
| |  | The research team will enroll subjects who are not yet adults (infants, children, teenagers) and will obtain written consent from the subject's parent(s) or guardian(s). (Complete sections 22 and 27) (Parent Permission Template) |
| |  | The research team will enroll adult subjects unable to provide consent (cognitively impaired individuals) and will obtain written consent from the subject's Legally Authorized Representative. (Complete sections 23 and 28) |

| NUMBER | ACTIVE DATE | PAGE |
|---------|-------------|----------|
| HRP-503 | 02-04-2020 | 26 of 44 |

| | |
|---------------------------------|--|
| 23.0 CONSENT PROCESS | 23.1 Where will the consent process take place? For Aim 1, participants will review an information sheet containing all elements of consent before the first GLA visit. They will indicate their consent to participate by logging on electronically to participate in the visit. For Aim 2, the consent process will occur at the participant's baseline visit, prior to completion of any study procedures. |
| | 23.2 Is there a waiting period available between informing the prospective subject and obtaining the consent? For Aim 1, participants will have time to read the information sheet and decide whether to participate or not before the GLA visit. For Aim 2, interested mothers will be contacted by the study staff via phone. Mothers will be provided information about the study procedures and inclusion criteria will be assessed. If inclusion criteria are met and a mother is interested in participating, a baseline study visit will be scheduled when the child is around 2 months of age. At this visit, informed consent will be obtained. |
| | 23.3 Describe: 
 The role of the individuals listed in the application as being involved in the consent process. The time that will be devoted to the consent discussion. Steps that will be taken to ensure the subjects' understanding. Steps that will be taken to minimize the possibility of coercion or undue influence. |
| | |

TEMPLATE: RESEARCH PROTOCOL

| NUMBER | ACTIVE DATE | PAGE |
|---------|-------------|----------|
| HRP-503 | 02-04-2020 | 27 of 44 |

Consent will only be obtained by trained study staff listed in the application as being involved in the consent process. Participants will be informed of the voluntary nature of their participation and the fact that refusal to participate does not in any way result in the reduction or denial of other home visiting services. They will be informed that the purpose of the study is to evaluate the effectiveness of an intervention targeting healthy infant feeding, and they will be informed regarding study procedures. They will also be told that HEMI visits will be digitally recorded for fidelity purposes. Participants will be informed that even if they agree to participate, they may withdraw their consent at any time without affecting the other services that they receive from ECS. Informed consent will be completed prior to the start of any study procedures. They will be given a copy of the consent form. Because of the possibility that some mothers will have limited literacy skills, we will read the procedures section to all mothers. Moreover, we will verbally reiterate that participation is voluntary, they can leave at any time, and that home visiting services will not be affected by their decision. A consent checklist has been developed to ensure that all components of consent are addressed.

For Aim 2, consent will be completed electronically via REDCap. The IRB approved consent will be modified to an electronic format in REDCap that includes all the same elements found on the paper document (i.e. IRB number, approval dates, and UC logo, etc.). The elements of the consent requiring a signature will be added as a generate field. The instrument includes fields to capture full name, signature, and date and time of the signature for the consenter, and witness and conditional text that states that all signatures are associated with the Subject ID# registered in the database. When completed REDCap will generate a footer that contains the long date and time the document was submitted and “Confidential” listed in the header as an added precaution to preserve the research participants confidentiality. Subjects will elect either a printed or electronic copy of the e-consent document.

If electronic consent cannot be completed via REDCap due to lack of accessibility to internet access, or due to comfort level with using technology, a paper copy of consent will be completed. Signed copies of the consent will be printed and kept secure with all printed files for this research study.

After completion of consent, they will then be randomized into the treatment or control condition. The consent process will take less than 30 minutes.

TEMPLATE: RESEARCH PROTOCOL

| NUMBER | ACTIVE DATE | PAGE |
|---------|-------------|----------|
| HRP-503 | 02-04-2020 | 28 of 44 |

23.4 Describe how consent of the subject will be documented in writing.

A written information sheet has been established for Aim 1. For Aim 1, documentation will be not be required since all study procedures are occurring virtually and the consent form would be the only document linking participant names to the study. For Aim 2, consent will be documented through the completed fields in the REDCap e-consent form. Documentation of consent is then stored within the REDCap online capture system and will be downloaded to our secure UC lab drive.

23.5 Describe the conditions under which you believe it would be appropriate to obtain ongoing consent from the subjects.

Ongoing consent will be obtained if significant study changes require participants to complete new study procedures or other unforeseeable study changes occur that may warrant ongoing consent.

| | | |
|--|--|---|
| 24.0 WAIVER OF DOCUMENTATION OF CONSENT | 
24.1 Justification for waiver of consent documentation. Check all that apply and provide rationale for all checked items. Please note that certain combinations of the selections below may justify a waiver of documentation. Please refer to HRP-411 – MEMBER CHECKLIST Waiver of IC Documentation to determine if your study qualifies for a waiver of documentation, and which boxes to check to justify the waiver.
 | |
| |  | N/A not requesting a waiver of documentation of consent. |
| |  | The research presents no more than minimal risk to subjects. The GLA phase (Aim 1) of the current study is considered minimal risk. These meetings will not be audio- or video-recorded and contact information will only be collected and used for those individuals expressing interest in participating in more than one GLA. Following the last meeting, all identifiable information linking GLA members to the study will be destroyed. |
| |  | Written information describing the research is to be provided to the subject, subject parent(s) or guardian(s), or subject Legally Authorized Representative. Written information describing the research will be provided to each participant via the Information Sheet. Research participants are encouraged to print this form, review it, and it for their records. |
| |  | Written information describing the research does not need to be provided to the subject, subject parent(s) or guardian(s), or subject Legally Authorized Representative. Not Applicable |
| |  | The research involves no procedures for which written consent is normally required outside of the research context. The research is limited to procedures for which written consent would not normally be required outside of the research context (i.e., online virtual meetings or phone calls). |
| |  | The only record linking the subject and the research would be the consent documentation. This part of the study (Aim 1) uses an online virtual meeting or phone call methodology and is not associated with more than minimal risk to participants. If signed consent were obtained, this would be the only identifying information linking the participant to their survey responses. |
| |  | The principal risk of a signed consent document would be the potential harm resulting from a breach of confidentiality. The rationale for changing the consenting procedure for Aim 1 (GLA) is that we have no credible need to collect and maintain the identities of our research participants beyond their participation in the planning meetings for the study. In doing so, we would introduce the unnecessary risk that an individual's identity could be connected to their data and input, and thus by collecting and maintaining signed consent forms, we introduce the potential risk of a breach of confidentiality that would not otherwise exist. |
| |  | The subjects are members of a distinct cultural group or community in which signing forms is not the norm. Not Applicable |

TEMPLATE: RESEARCH PROTOCOL

| | | |
|--------|-------------|------|
| NUMBER | ACTIVE DATE | PAGE |
|--------|-------------|------|

| | | |
|---------|------------|----------|
| HRP-503 | 02-04-2020 | 30 of 44 |
|---------|------------|----------|

| | |
|--|---|
| |  There is an appropriate alternative mechanism for documenting that informed consent was obtained. Participants will be presented with an Information Sheet, but it will not require the participant to sign the form. Instead, participants will agree to participate by continuing with study procedures (i.e., online virtual meeting or phone call) after receiving the Information Sheet. If they decline to participate, they will not be asked to continue on with the GLA meetings. |
| |  The research is not FDA-Regulated. |
| |  The written script of the information to be provided orally, electronically, or on paper (information sheet) includes all required and appropriate additional elements of consent disclosure. When requesting a waiver of documentation, an information sheet is required. This box should always be checked for a waiver of documentation. (Follow HRP-502I TEMPLATE Information Sheet) Participants will be sent the Information Sheet that is identical to a conventional informed consent form and contains all necessary information. |
| |  Other  DescribeNot applicable |
| | |

| | |
|---|--|
| 25.0 WAIVER OR ALTERATION OF CONSENT PROCESS | 25.1 Justification for waiver or alteration of the consent process. Check all that apply and provide a rationale/explanation for all checked statements. Please note that certain combinations of the selections below may justify a waiver of or alteration of consent. Refer to HRP-410 – MEMBER CHECKLIST Waiver of IC Process to determine if your study qualifies for a waiver or alteration of consent, and which boxes to check to justify the waiver or alteration. |
| |  N/A Not requesting a waiver or alteration of consent process. |
| |  The research does NOT involve non-viable neonates. Rationale/Explanation |
| |  The research involves no more than Minimal Risk to subjects. Rationale/Explanation |
| |  The research could NOT practicably be carried out without the waiver or alteration. Rationale/Explanation |
| |  The waiver or alteration will NOT adversely affect the rights and welfare of the subjects. Rationale/Explanation |
| |  Whenever appropriate, the subjects will be provided with additional pertinent information after participation. Rationale/Explanation |
| |  The research is NOT FDA regulated. Rationale/Explanation |
| |  Other  Describe any other reasons/explanations for request of waiver/alteration |
| | |

| NUMBER | ACTIVE DATE | PAGE |
|---------|-------------|----------|
| HRP-503 | 02-04-2020 | 31 of 44 |

| | |
|---|---|
| 26.0 CONSENT OF NON-ENGLISH- SPEAKING SUBJECTS | 26.1 Indicate what language(s) other than English are understood by prospective subjects or representatives. (Please note that if non-English speaking subjects will be consented, translated consent forms must be uploaded into the consent section of the RAP Smart Form. For Greater than minimal risk studies, a third-party translation certificate is also required. For minimal risk studies, the consent must be translated by someone independent of the study team and their credentials should be provided.) Participants will be enrolled who are English or Spanish speaking, and therefore consent will be done in English and Spanish. A letter has been uploaded with the credentials of the translators who translated the Information Sheet and Consent Form into Spanish, and the Spanish version of these documents has been uploaded. |
| | 26.2 If subjects who do not speak English will be enrolled, describe the process to ensure that the oral and written information provided to those subjects will be in that language. Indicate that language that will be used by those obtaining consent. Spanish speaking families will be enrolled. They will complete consent using a consent document in Spanish and consent will be completed with a Spanish speaking researcher. All elements of the consent process will be completed in Spanish. |
| | |
| | |

| | |
|--|---|
| 
27.0 CONSENT OF SUBJECTS WHO ARE NOT YET ADULTS (infants, children, adolescents)
 | 
27.1 Describe the criteria that will be used to determine whether a prospective subject has not attained the legal age for consent to treatments or procedures involved in the research under the applicable law of the jurisdiction in which the research will be conducted (e.g. individuals under the age of 18 years (Ohio))
 
Participants recruited for Aim 2 (only) are infants whose mothers will be consented only if they are at least 18 years of age. We will also include this in the discussion and verification of inclusion criteria in the written informed consent document. Aim 1 participants are all adults over 18 years of age.
 |
| | 
27.2 Describe whether parental permission will be obtained. (Parent Permission Template)
 
Parent permission will be obtained from:
 
 • One parent even if the other parent is alive, known, competent, reasonably available, and shares legal responsibility for the care and custody of the child. |
| | 
27.3 Describe whether permission will be obtained from individuals other than parents, and if so, who will be allowed to provide permission. Describe the process used to determine these individuals' authority to consent to each child's general medical care.
 
The ECS program from which participants are recruited only enrolls legal guardians and their children, and therefore it is known that all mothers are the legal guardian.
 |
| | 
27.4 Indicate whether assent will be obtained from all, some, or none of the children. If assent will be obtained from some children, indicate which children will be required to assent. (HRP-502Y Youth Assent or Medical Assent Template)
 
Assent will not be required as children enrolled in this study are infants.
 |
| | 
27.5 When assent is obtained, describe whether, and how, it will be documented.
 
Not Applicable
 |
| | |
| | |

TEMPLATE: RESEARCH PROTOCOL

| | | |
|---------|-------------|----------|
| NUMBER | ACTIVE DATE | PAGE |
| HRP-503 | 02-04-2020 | 33 of 44 |

| | | |
|--|--|--|
| 28.0 CONSENT/ASSENT OF COGNITIVELY IMPAIRED ADULTS | 28.1 For potentially cognitively impaired adults, describe the process to determine whether an individual is capable of consent. | |
| | Not Applicable | |
| | 28.2 List the individuals from whom permission will be obtained in order of priority. (Please note that the consent form will require revision to add a signature line for LAR and authority of LAR). | |
| | Not Applicable | |
| | 28.3 Describe the process for assent of the subjects. Indicate whether assent will be required for all, some, or none of the subjects. If some, indicate which subjects will be required to assent and which will not. | |
| | Not Applicable | |
| 28.4 If assent will not be obtained from some or all subjects, explain why. | | |
| Not Applicable | | |
| 28.5 Describe whether assent of the subjects will be documented and the process to document assent. | | |
| Not Applicable | | |
| 29.0 HIPAA | 29.1 If you will use hospital or other healthcare provider records, data from a research data repository or any other information maintained by a hospital, academic medical center, or another healthcare entity, how will you gain access to the information? (check all that apply, i.e. if you will request a waiver for screening and obtain a signed authorization upon enrollment, check both). | |
